10.6 Secondary Efficacy Analyses

All analyses of secondary endpoint DriveCam data will be analyzed using GEE. GEE analyses assuming a Poisson distribution and natural logarithmic link function will be used to analyze individual DriveCam events per participant (random effect) and assess the relative risk of each dichotomous outcome (i.e., presence/absence of long-glance, crash/near crash per event). For these secondary analyses, relative risk ratios with 95% confidence intervals will be computed rather than testing statistical significance (Zou, 2004). Note that the widths of confidence intervals will not be adjusted for multiple comparisons and no definite conclusions can be drawn from these results.

11 Safety Analyses

The PI ([name]) will be responsible for detecting, documenting, and reporting events that meet the definition of an Adverse Event (AE) or Serious Adverse Event (SAE). Safety data will be tracked and reported as required by Clinicaltrials.gov. Three tables summarizing adverse events will be created:

- All-Cause Mortality: A table of all deaths due to any cause, with number and frequency of such events in each arm/group of the clinical study.
- Serious Adverse Events: A table of all serious adverse events with number and frequency of such events in each arm/group of the clinical study. See Serious Adverse Events definition

below.

- Other (Not Including Serious) Adverse Events: A table of events within any arm of the clinical study with number and frequency of such events in each arm/group of the clinical study. See Adverse Events definition below.

These events will be analyzed and reported for All Randomized Study Participants and by treatment group at the end of the study period. The only SAE that will be analyzed in the interim is events with a shock value (i.e., indicating a collision) as recorded by DriveCam technology (See 8.5 Interim Analyses for more information).

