5.1 Study Objectives

The goal of the proposed research is to empirically test the effectiveness of the FOCAL+ intervention in comparison to a sham intervention at improving visual attention and driving performance in teens with ADHD. Specifically, we will conduct a randomized controlled trial using 152 teens diagnosed with ADHD. Teens will be randomized to receive 5 training sessions of the FOCAL+ intervention or a sham intervention. 1-month and 6-months post-training, teens' driving skills, including frequency of extended eye glances, will be assessed during driving simulation. In addition, at the conclusion of training, a DriveCam camera system in their car will record naturalistic driving. The DriveCam will remain in their car until 12-months post-training. Finally, we will acquire the teen's driving records for the period they are in the study.

Primary Objective: We will examine the effectiveness of the FOCAL+ intervention versus sham intervention at decreasing rates of extended glances away from the roadway and improving driving performance among teens with ADHD at 1-month post-training, and 6-months post-training.

Secondary Objective: We will examine the effectiveness of the FOCAL+ intervention versus sham intervention in decreasing rates of extended glances away from the roadway, frequency of driving events, crashes, and crashes/near crashes as measured by in-car technology (DriveCam) during the 12-months post-training.

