The DriveCam device has two integrated cameras. One facing the forward roadway; the other facing the driver. If the built-in accelerometer detects a ≥ 0.6 forward or lateral g-force event, the device records the 8 secs before and 4 secs after the triggered event. Four events will be randomly selected for coding if a teen had >4 events in a week. Trained coders will code the onset and offset of visual glances away from the roadway such that a count of extended eye glances (≥ 2 seconds) will be obtained. Additionally, coders will record whether the event captured a crash (i.e., contact between the vehicle and another object) or near crash (i.e., an evasive maneuver performed to avoid a MVC). The two secondary endpoints that will be used from the DriveCam video events will be as follows:

1) Events that Included an Extended Eye Glance: During the 5-seconds preceding the event until the 1-second after the g-force event, if a glance away from the roadway was ≥ 2 seconds, the event will be identified as having a long glance. Events that do not include a glance away from the roadway ≥ 2 seconds during the 5-seconds preceding the event until the 1-second after the g-force event will be identified as not having a long glance.

2) Events that Included Crashes and Near Crashes: Coders will make a determination after viewing each event whether the event included or did not include a crash or near-crash. Crashes and near crashes (CNC) will be combined due to low crash rates and near-crashes are an established surrogate for crashes (Guo, Klauer, Hankey, & Dingus, 2010).

6 Study Methods

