6.4 Study Assessments

Frequency and Timing of Relevant Assessments:

	Baseline/Randomization	1-month follow-up assessment	6-month follow-up assessment	12-month follow-up
Diagnostic and Clinical Assessment	X			
Driving Simulation Assessment		X (2 runs)	X (2 runs)	
DriveCam Recording	X (Installation)	← CONTINUOUS →		
Driving Records		← CONTINUOUS →		
Adverse event monitoring		← CONTINUOUS →		

Analysis Time Windows:

Visit (target day)	Lower bound (days)	Upper bound (days)
Baseline/Diagnostic and Clinical Assessment (-7)	-14	-7
Randomization/Training 1 (0)	N/A	N/A
Training 2 (7)	4	10
Training 3 (14)	11	17
Training 4 (21)	18	24
Training 5 (28)	25	31
Month 1 (30 post-training 5)	30	45
Month 6 (180 post-training 5)	180	195
Month 12 (360 post-training 5)	Not in person	Not in person

Study Variables:

Primary Endpoint Variables Collected During Secondary Task (ST) Performance Portion of Driving Simulation:

1) Extended eye glances: This variable will be a frequency count of the number of ≥ 2 secs glances. Extended eye glances of interest are those occurring during the ST portions of the drive. The range for this variable could range from 0 to 100.

2) Standard Deviation of Lane Position (SLDP): Standard deviation of lane position will be calculated during the ST portions of the drive. An average of 0 indicates that an individual maintained consistent lane position. The range for this variable is from 0 to 3

Secondary Endpoint Variables Collected using DriveCam:

1) Extended eye glances: As has been done in previous research, the number of ≥ 2 sec eye glances away from the roadway occurring between -5 secs before to 1 sec after the event causing a .6 g-force will be calculated (Dingus, Klauer, Neale et al., 2006). For each event video, we will code the onset and offset of glances away from the roadway. Based on the onset and offset times, we will calculate whether the video clip contains a continuous eye glance away from the roadway that lasts for 2-seconds or longer between -5 secs before to 1 sec after the event. It is possible that some participants will not contribute any data at all to this outcome variable due to not experiencing any .6 g-force events during the 12-month observation. The lower end of the range for this variable for participants who do experience at least 1 .6 g-force event during the observation period is 0. There is no upper limit to this variable.

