2) Crashes and near crashes (CNC): Like the extended eye glance endpoint, this variable is only calculated when participants experience a g-force event $\geq .6$. Coders will record whether the event captured a crash (i.e., contact between the vehicle and another object) or near crash (i.e., an evasive maneuver performed to avoid a MVC). Some participants may not contribute data due to not having any events. These participants will not be included in analyses. The lower end of the range for this variable, for participants who do experience at least 1 .6 g-force event during the observation period is 0. There is no upper limit to this variable.

7 Sample Size

Our initial protocol proposed to randomize 136 participants; however, this randomization goal did not account for attrition at the 1- and 6-month driving simulations—the source of our primary endpoints. When we reached a sample size of 136, we estimated how many additional participants would be required to achieve 136 participants with completed driving simulation data at 1- and 6-months post-training. The calculation suggested that we needed to recruit a randomized sample size of 152 to achieve 136 participants with 1- and 6-month simulator outcomes (primary endpoints). (See Section 16 for date of this protocol change).

8 General Analysis Considerations

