8.2.2 Per Protocol Population

- DriveCam outcomes: All participants who produce any DriveCam events during the period beginning at post-training through 1-year post-training. For any participants with missing DriveCam 'long-glance' data, data will be assumed to be missing at random and handled using multiple imputation.

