8.2.3 Safety Population

All subjects who have a DriveCam installed in their car will be monitored for safety as described in 8.5 Interim Analyses.

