8.3 Covariates and Subgroups

For all analyses:

- Driving experience: Defined as baseline date minus the date that the teen received their graduated or full unrestricted license. Computed in months.

Specific to driving simulation analyses:

- Driving runs: Included in order to be able to include primary outcomes from the two driving runs conducted at the baseline, 1-month post-training assessment, and the 6-month post-training assessment. Generalized estimating equation (GEE) analyses allowed driving simulation data from the two "runs" nested within each of the three "drive types" nested within each participant to be modeled as correlated response variable data, but main or interaction effects for "runs" were not of theoretical interest.

Specific to DriveCam analyses:

- To account for variability in the length of time the DriveCam camera was installed in each participants' automobile during the 1-year post-training period was included as a covariate in addition to months of driving experience as detailed above.

Supplemental Analyses (Requested by New England Journal of Medicine reviewers, editor, and/or statistical expert)

- Moderation Effects—These analyses are post-hoc; thus, effects (adjusted mean difference or relative risk and 95% CI) will be reported rather than significance testing. Note that the widths of confidence intervals are not adjusted for multiple comparisons and no definite conclusions can be drawn from these results.

- Medication status dichotomized based on whether the teen reported taking ADHD medication at any point during the 12-months of naturalistic driving.
- COVID-19 Sensitivity Analysis
 - For 56 (FOCAL+: n=29 teens; Control: n=27 teens) of the 152 participants, their 1-year of naturalistic driving included days beyond March 15, 2020 when COVID restrictions were put into place. We will conduct a sensitivity analyses of our naturalistic driving results by re-running our primary and secondary analyses but including only the 96 teens (FOCAL+ n=47; Control n=49) whose 1-year of naturalistic driving ended prior to COVID restrictions.

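### The secondary objective is to reduce the frequency of driving events and crashes on DriveCam, but the only planned DriveCam efficacy estimate is a risk per g-force event

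*Combined protocol and SAP*

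**What the plan says.** SAP 5.1 states the secondary objective as "decreasing rates of extended glances away from the roadway, frequency of driving events, crashes, and crashes/near crashes as measured by in-car technology" over the 12 months after training.

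SAP 5.2 turns this into two DriveCam endpoints. Each is a yes/no label on an event that has already triggered the camera at 0.6 g or more: did the clip contain a long glance, and did it contain a crash or near crash? Coding is capped: "Four events will be randomly selected for coding if a teen had >4 events in a week".

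SAP 8.4 confirms that both outcomes are binary. SAP 10.6 analyses individual events by GEE (Poisson, log link) to "assess the relative risk of each dichotomous outcome (i.e., presence/absence of long-glance, crash/near crash per event", reported with unadjusted 95% confidence intervals and no significance test.

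On who and what enters the model:
- SAP 6.4, for crashes/near crashes: "Some participants may not contribute data due to not having any events. These participants will not be included in analyses".
- SAP 8.2.2 defines the DriveCam population as "All participants who produce any DriveCam events during the period beginning at post-training through 1-year post-training".
- SAP 8.3 says that the time the camera was installed in the "automobile during the 1-year post-training period was included as a covariate in addition to months of driving experience". It is not a denominator or offset.

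**The concern.** The objective asks whether trained teens have fewer events and fewer crashes. The analysis asks a different question: once a g-force event has happened, how likely is it to be a crash/near crash or to contain a long glance? The second answers the first only if training leaves the number of g-force events unchanged. Yet reducing driving events is itself part of the objective.

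DriveCam is the only real-world efficacy source left, because SAP 14.6 (1/11/21) drops motor vehicle bureau crash records. A relative risk below 1 reported under a frequency objective invites the conclusion that crashes fell. A relative risk near 1 invites the conclusion that nothing changed. Neither follows from a risk per event.

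**Working it through.** The plan gives no figure to reproduce here. The check is a comparison of sections, then an identity with assumed inputs.

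**Objective against analysis (current SAP only)**

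| Term in the 5.1 objective | Endpoint in 5.2 | Efficacy analysis in 10.6 |
|---|---|---|
| Frequency of driving events | none | none |
| Frequency of crashes | none for crashes alone | none |
| Frequency of crashes/near crashes | yes/no per event | relative risk per event |
| Rates of extended glances | yes/no per event | relative risk per event |

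The last row is weaker evidence, since a rate of glances could be read as a percentage of events. The point rests on the frequency terms.

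**Identity.** Write CNC for crash/near crash. Then CNC frequency = event frequency × P(CNC given an event). Dividing FOCAL+ by sham:

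per-event RR = a / E, where a = CNC rate ratio and E = event rate ratio.

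This is exact for fully coded, unadjusted events. The cap and the covariates make it approximate.

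**Assumed inputs** (the documents give no event rates by arm):
- a = 0.75: E = 0.9 gives 0.83; 0.8 gives 0.94; 0.75 gives 1.00; 0.7 gives 1.07. A benefit shrinks, vanishes or reverses.
- a = 1.3, E = 1.3: 1.3/1.3 = 1.00. An increase does not show.
- a = 1: E = 1.1 gives 0.91; 1.2 gives 0.83; 1.3 gives 0.77. There is an apparent benefit with no fewer crashes/near crashes.

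**When it matters little or much.** Let p0 be the CNC share of sham events (assumed 5%, 15%, 30%) and b the rate ratio for other events. Then E = p0·a + (1 − p0)·b.

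| Case | p0 = 5% | 15% | 30% | True CNC rate ratio |
|---|---|---|---|---|
| Only CNC events fall (a = 0.75, b = 1) | 0.76 | 0.78 | 0.81 | 0.75 |
| Only CNC events rise (a = 1.3, b = 1) | 1.28 | 1.24 | 1.19 | 1.30 |
| Only other events fall (a = 1, b = 0.8) | 1.23 | 1.20 | 1.16 | 1.00 |
| Only other events rise (a = 1, b = 1.3) | 0.78 | 0.80 | 0.83 | 1.00 |

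The gap is small if training acts on crashes/near crashes alone, and larger if it acts on other events.

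**How far the cap disturbs the identity.** Assume equal numbers of teens with 0.5 and 8 events per week (Poisson), CNC shares of 20% and 5%, and a 40% cut in the busy teens' events, to 4.8.
- All events: the CNC rate goes from 0.1 + 0.4 = 0.5 to 0.1 + 0.24 = 0.34, so a = 0.68. Events go from 8.5 to 5.3, so E = 0.62. Per-event RR = 1.09.
- Coded events: the expected coded number per week is 0.50 for quiet teens, and 3.94 falling to 3.51 for busy teens. The CNC share goes from 0.0669 to 0.0687, so RR = 1.03.

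The true CNC rate ratio is 0.68. Neither 1.09 nor 1.03 conveys it.

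**The case against.** **The SAP is nearly consistent.** Sections 5.2, 8.4, 10.6 and 14.7 agree on a binary outcome per event, 10.6 says so openly, and the outlier is mainly one sentence in 5.1. This stands. It is why a wording change is enough to remove the contradiction, but it does not make the objective answered.

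**Little inferential weight rests on it.** The outcome is secondary, with confidence intervals only and a statement that no definite conclusions can be drawn (8.5.5, 10.6). This also stands. It limits how strongly the result may be claimed, not the risk of misreading what was estimated.

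**Crashes are counted elsewhere.** Crash counts by arm are reviewed monthly, with a provision for ending the study early (8.5.1, 8.5.3, 8.5.8). They probably also appear in the end-of-study adverse event tables for all randomized teens (section 11). With 1:1 allocation these have comparable person denominators. A reader might infer that harm from crashes would go unseen; the documents do not support that. What is missing is exposure time and near crashes.

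**Stronger readings to avoid.** A reader might infer that leaving out teens with no events biases the relative risk. It does not shift a per-event risk; it only means that no rate can be read from that set. Camera time as a covariate is likewise no error in a per-event model. The 6.4 statement "There is no upper limit to this variable", which suits a count rather than a yes/no label, is a separate drafting matter. The protocol's earlier per-hour DriveCam rates (5.f.2.a) were replaced by the SAP's models, and this point does not rest on them.

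**Conclusion.** The mismatch is real and lies within the current SAP: 5.1 names frequencies, while 5.2, 8.4 and 10.6 estimate only risk given a g-force event. It should be fixed. The per-event relative risk is a legitimate quantity, but it does not show whether events or crashes/near crashes became less frequent.

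Under the assumed inputs, a true 25% fall in crashes/near crashes could read anywhere from 0.83 to 1.07. Unchanged crash/near-crash frequency could read 0.91 to 0.77 if events rise 10 to 30%. These are illustrations. A reader might infer that the trial's DriveCam result is wrong or that it conceals harm; without event rates by arm, the documents support neither, and if only crashes/near crashes changed the discrepancy would be small. The simulator incidence rate ratio in 10.5 compares counts, but it is not DriveCam evidence.

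**What to change.** 1. **Minimum, sufficient to remove the contradiction.** In 5.1 and 10.6, state that the DriveCam relative risk is conditional on an event of at least 0.6 g. Restate the secondary objective and its conclusions to match, dated, with the original objective left visible. Do not describe the result as fewer crashes or fewer events. Cost: wording.

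2. **If event totals were kept, add a rate analysis**, dated and labelled post hoc. Fit a per-teen log-link Poisson model with robust standard errors for all events of at least 0.6 g, and for crash/near-crash events coded by the blinded coders. Use as offset the log of days the camera was installed or operational, and adjust for months of driving experience. Include randomized teens with a camera, counting no events as zero. The 8.2.3 safety population already describes such a set: "All subjects who have a DriveCam installed in their car will be monitored for safety as described in 8.5 Interim Analyses". Weight coded events for the four-per-week cap where weekly totals exist; otherwise state the cap as a limitation.

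3. **Disclose selection.** Having a camera may itself be decided after randomization: 6.1 lists installation among post-intervention steps, while the 6.4 schedule places it at baseline. Report by arm the numbers with no camera and with zero events, which 8.4 now groups together.

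4. **Use blind-coded crashes only.** The shock-trigger clips in 8.5.1 are reviewed by a researcher who knows allocation, whereas 6.3 keeps the DriveCam coders blind. Those clips should not supply an efficacy crash count.

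5. **Check event capture first.** SAP 14.6 records a lower threshold and overloaded servers, with the threshold set back on 3/26/19. SAP 14.8 logs a further threshold change on 3/23/2018. Establish completeness across both before choosing any cut date. Treat exclusion of time before 3/26/19 as a sensitivity analysis only.

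**Cost and limits of items 2 to 5.** The rate model is post hoc and may not be feasible: the documents do not say that weekly totals were kept, and video is destroyed after the study (11.5). Camera days are only a proxy for teen driving time, since footage of other drivers is destroyed and the GPS data are not accessed.

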The two outcomes for the secondary analyses, off-road glances and crash/near crash were both measured on a binary scale. Some participants did not have any events either due to the DriveCam not being installed in their car or they did not have any events. Such missing data was not imputed, and we conducted non intent-to-treat analysis using those participants with event data. There was no missing data for the ‘crash/near crash’ secondary outcome across events for those with a DriveCam installed. The GEE analysis for the ‘crash/near crash’ outcome was performed using all

participants with DriveCam event data available. However, long glance data was missing for some events due to unforeseen circumstances (e.g., DriveCam view obstruction or participant driver was wearing sunglasses). Missing data for the 'long-glance' outcome was imputed using GEE model-based imputation. Specifically, a logistic link function was used within a missing data imputation model that allowed the effect of random assignment to predict the presence (=1) or absence (=0) of long-glances nested within participants while controlling for months of driving experience and days DriveCam was operational in vehicle.

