9.5 Subject Disposition

Operational definitions used to establish how many subjects reached the various stages of the trial are listed below:

- 1) Number Screened: Screening for the study will be defined as any contact between an interested individual who queries about the study and is screened for potential eligibility as

described in 6.1 Recruitment. We will track the number of individuals who are screened for the study.

[figure not shown]
- 2) Consent: Consent will occur during the first study visit (also known as Baseline/Diagnostic and Clinical Assessment).
- 3) Number Eligible: Of those who consented to the study, the number who met all eligibility criteria and who showed up for the initial training visit (when randomization occurred).
- 4) Randomized: Randomization will occur at the second study visit. A sealed envelope will contain the participant's randomization
- 5) Completed intervention/training visits 1-5: Participants will be considered to have completed the intervention/training visit if they complete at least 1 training.
- 6) Completed study 1-month post-training follow-up: Participants will be considered to have completed the 1-month post-training follow-up visit if they complete at least one of the two assessment drives.
- 7) Completed study 6-month post-training follow-up: Participants will be considered to have completed the 6-month post-training follow-up visit if they complete at least one of the two assessment drives.
- 8) Completed DriveCam follow-up: Participants will be considered to have completed the DriveCam follow-up if we are able to obtain DriveCam data within the previously specified analysis time window (See 6.4 Study Assessments section).

We will track many subjects reached the various stages of the trial, how many dropped out and for what reasons (death, treatment failure, withdrew consent).

Resolving multiple or ambiguous visit dates

Research assistants will be trained to keep detailed logs of each study visit noting any deviations in the study visit protocol (e.g., visit rescheduled because teen took their stimulant medication). If there is any ambiguity arising from multiple sources of visit date, we will examine research visit logs to understand the reason for multiple visits. Using this information, we will decide which visit data to use in final analyses.

Skeleton CONSORT flow diagram

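### Section 11 puts camera-detected collisions over all randomised teens, although some had no camera and camera time varied, so a reported collision frequency would tend to be too low

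*Combined protocol and SAP*

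**What the plan says.** SAP section 11 plans three tables (deaths, serious adverse events, other adverse events), each with counts and frequencies by arm. On the population it says: "These events will be analyzed and reported for All Randomized Study Participants and by treatment group at the end of the study period." It then names the one serious adverse event to be examined during the trial: "events with a shock value (i.e., indicating a collision) as recorded by DriveCam technology." Section 11.5, item 7, lists crash involvement as an anticipated adverse event and only refers the reader to section 8.5, the monthly DriveCam review.

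Four other places bear on who was under camera observation:

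- Section 8.2.3 (Safety Population): "All subjects who have a DriveCam installed in their car will be monitored for safety as described in 8.5 Interim Analyses."
- Section 8.4 (missing data, secondary analyses): "Some participants did not have any events either due to the DriveCam not being installed in their car or they did not have any events."
- Section 8.3 adds a covariate to the DriveCam efficacy models because of "variability in the length of time the DriveCam camera was installed."
- Section 14.8 (11/17/2020) says cameras may stay in beyond one year, and that installation and removal visits were postponed during the shelter-in-place order.

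There are also routes that need no camera. Protocol section 6.e has participants asked about adverse experiences at each assessment visit. SAP section 6.4 shows continuous adverse event monitoring without naming a method. Section 6.2 repeats a Driving History Questionnaire at 6 and 12 months, but the text does not say that it asks about crashes.

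**The concern.** A teen without a camera adds one to the section 11 denominator but has little chance of adding a minor collision to the numerator. The same holds for the part of follow-up when a camera was absent. The table would then show no collision where the truth is that nobody was looking. The sentence quoted from section 8.4 groups teens with no camera together with teens who had a camera and no event. Only the second group are observed zeros.

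Collision is the one harm that the plan singles out for monthly review by an unblinded researcher, with possible termination (sections 8.5.1 and 8.5.3). The end-of-study table is where a reader would look for its absolute frequency, so that table should show who was observed and for how long.

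**Working it through.** **Which collisions depend on the camera.** Section 5.2 codes a crash as any contact between the vehicle and another object. Section 11.6 defines a serious adverse event by its outcome, such as death, hospitalisation or lasting disability. Collisions that meet 11.6 are the likeliest to be learned at visits, so the gap lies mainly in minor ones. The plan does not settle whether a minor collision goes in the serious or the other table, but both use all randomised teens.

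**Whether another planned table gives number at risk and exposure.**

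- Section 8.5.8 (monthly templates): counts by arm only.
- Section 9 (general rule): summary tables carry the relevant population size and missing observations. This may show a number of teens, but not camera-days.
- Section 9.5, stage 8: teens are taken to have "completed the DriveCam follow-up if we are able to obtain DriveCam data within the previously specified analysis time window." The month-12 row of that window in section 6.4 has no day bounds, and camera-days are not reported.
- Section 10.6 (DriveCam efficacy): the analysis is per event and combines crashes with near crashes. Section 8.4 restricts it to teens with event data. It yields no collision rate per teen or per unit of time.

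None gives camera-days.

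**Direction and possible size.** The plan states no collision rate, so there is none to reproduce. The number randomised checks out from section 8.3: 29 + 47 = 76 and 27 + 49 = 76, total 152. Let f be the share of randomised teens with a camera and t the mean camera-years per equipped teen. Counting camera-detected collisions only:

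collisions / 152 = f × t × (collisions per camera-year)

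The shortfall is therefore 1 − f × t. The documents give neither f nor t, so the values below are assumed and purely illustrative. The count of 100 is a round figure; section 14.6 reports more than 100 DriveCam-coded crashes in a year, and not all of these need enter the adverse event tables.

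| f | t | Per randomised teen | Per camera-year | Shortfall |
|---|---|---|---|---|
| 1.00 | 1.00 | 100/152 = 0.66 | 0.66 | 0% |
| 0.95 | 1.00 | 0.66 | 0.69 | 5% |
| 0.90 | 0.90 | 0.66 | 0.81 | 19% |
| 0.80 | 0.75 | 0.66 | 1.10 | 40% |

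Collisions learned by other routes would reduce the shortfall. So would camera time beyond a year, if collisions then are counted: with f = 0.95, a mean t of 1/0.95 = 1.05 would cancel it.

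**Arm comparison.** With equal true rates, the apparent ratio is the ratio of f × t between arms. Equal coverage gives 1.00. An assumed 0.85 against 0.95, with the same t, gives 0.85/0.95 = 0.89. For scale, 100 collisions split evenly give a standard error of the log ratio of √(1/50 + 1/50) = 0.20, and a 95% range of exp(±1.96 × 0.20) = 0.68 to 1.48. Clustering of collisions within teens would widen that range. The only arm-level figures near this question are for follow-up running into COVID restrictions ("For 56 (FOCAL+: n=29 teens; Control: n=27 teens) of the 152 participants"): 29/76 = 38% against 27/76 = 36%. They are nearly balanced, and they do not measure camera coverage.

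**The case against.** The strongest reply is that the plan has two sets for two purposes. Section 8.2.3 ties the camera-equipped set to the monthly review, and section 11 separately names all randomised teens, a conventional choice for deaths and adverse events. A reader might infer that the two sections contradict each other. The text does not support that. They are two sets that the plan does not reconcile for the one harm both cover.

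The second reply is that no text says every shock clip becomes a table row, and that frequency is left undefined. This stands, and it is why the point concerns a collision frequency if one is reported. But section 11 itself calls these events a serious adverse event, and 11.5 lists crash involvement, so inclusion is the natural reading.

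Third, the annotation rule in section 9 may already show the relevant population size. That covers part of the gap and leaves exposure time uncovered.

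Fourth, the direction is not certain, because some cameras may have stayed beyond a year. This is fair, and it is why the frequency is said only to tend to be too low.

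A reader might also take the 19 crashes in driving records against more than 100 on DriveCam (section 14.6) as the fraction caught without a camera. The documents do not show that the 19 are among the more than 100. The records can include crashes of teens without cameras, and they are only one route. The comparison gives no detection probability and is not used here.

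**Conclusion.** The point holds as a minor one about the absolute collision frequency at the end of the study. Following section 11 as written counts unobserved teens and unobserved time as collision-free, and no planned safety table gives the camera-days needed to correct for this. The likely direction is downward, mainly for minor collisions. This rests on two statements in the SAP, that some teens had no camera and that installed time varied, and on the inference that minor collisions are less often learned by other means. The size cannot be computed; the figures of 0% to 40% only show how the shortfall depends on assumed coverage.

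Two stronger conclusions might be drawn, and neither is supported. One is that the comparison between arms is biased. That needs coverage or camera time to differ by arm, which is neither shown nor excluded. The other is that the stopping review is compromised by these tables. It uses its own monthly counts.

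**What to change.** In section 11, report DriveCam-detected collisions by arm for teens with a camera installed, whether or not they had an event. For each arm give:

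- the number of teens at risk;
- total camera-days in the post-training follow-up;
- teens with at least one collision;
- collisions per camera-day.

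List collisions learned by other routes separately, for all randomised teens. Keep all randomised teens as the denominator for deaths and all other adverse events.

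The cost is SAP wording and a few table rows. Camera status and days installed are already needed for the DriveCam analyses in sections 8.3 and 8.4, so no new data collection is required. The downside is a second collision listing to explain and slightly higher reported frequencies.
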